1.0 Objectives / Specific Aims

- The purpose of this study is to evaluate the effectiveness of cholesterol/lovastatin versus lovastatin alone to treat porokeratosis. Our working hypothesis is that both topical cholesterol/lovastatin and lovastatin alone are helpful in treating patients with disseminated superficial actinic porokeratosis (DSAP).
- Aims:
 - 1. To evaluate the response to treatment with topical cholesterol/lovastatin and lovastatin alone in a series of patients with the diagnosis of DSAP.
 - 2. To characterize lesion patterns following topical treatment and patterns of lesion regression.

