10.0 Study Design / Methods

- Potential subjects will be approached for informed consent as directed in sections 8.0 and 9.0. Pertinent project information, risks, and time commitment will be relayed to subjects. If subjects show interest in participating, they will be given consent forms to either sign or bring home for consideration. A urine pregnancy test will be administered to these patients to confirm that they can be included in the study.
- If the patient is eligible for the study, he or she will be randomly assigned to one of two groups. They will have a 50/50 chance of being in either group. Neither the researchers nor you will make the choice to which group you are assigned. The two groups are Group A (cholesterol/lovastatin) and Group B (lovastatin only). The patient will not be informed of which group they are in and will not be informed of what their study medication is, allowing single-blinding. Researchers will not be masked.
- Enrolled subjects will be followed up at monthly intervals for three months via virtual check-in using an MUSC approved HIPAA compliant technology. At each visit, participants will undergo brief, limited physical examination (in order to determine disease severity and affected body surface area); additionally, clinical photographs of the lesion will be obtained in clinic or shared virtually with the investigators via secure email (sent to MUSC Outlook email). The physical exam will occur in-person or by using the virtual visit technology, which allows us to see the patient and visualize their skin findings.. Photographs will be stored in the coded study-specific medical record for further analysis of lesion features.
- At each visit a Patient Quality of Life, Physician Global Assessment Scale, and Actinic keratosis Field Assessment Scale will be administered.
- Patients will be contacted via virtual check-in visits at weeks 4, 8, and 12. Patients will be asked about compliance and any adverse effects experienced. Patients are also encouraged to contact [name] at any given point during the study if they think they are experiencing study-related side effects. Immediate consultation will follow to determine the severity of such event and necessary impacts on patient health and participation. Participants will also be contacted by phone by study team member to assess for any adverse effects at weeks 2 and 6 of treatment.

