11.0 Data Management

- Continuous data will be summarized using descriptive statistics (number of values, means, standard deviation, median, minimum and maximum). Categorical data will be summarized using frequency tables (frequencies and percent).

- We are comparing before and after photographs from the same patient, hence we employ analysis by paired t-test to compare baseline data with data after treatment.
- Coded dermoscopic and clinical photographs may be obtained for further analyses. Files with patient images will be stored in a secure departmental drive that will only be accessible to study team members by their unique MUSC ID and password.
 - Photos shared directly via email to study team members will be also be uploaded to the participants respective coded folder on the Box drive.
 - These emailed photos (sent by the participant personal email) must be de-identified close up photos of the participants legs or arms, and sent only to study team members secure MUSC-assigned Outlook email addresses. Photos that do not fit this criteria will be deleted upon receipt and not used in the study.
- All subject medical record information and data collection will be coded and stored on an MUSC Box drive only accessible to study team members, and will be protected by two-factor authentication.

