6.1 Primary outcome

The primary analysis will compare the improvement in DSAP-GASI scores before treatment and after treatment in both groups. Only participants with clearly documented photos across all visits will be considered for the DSAP-GASI efficacy analysis. The scores will be graded by two blinded, trained physicians. Cronbach's Interrater reliability will be calculated among raters across visits and the scores will be averaged for each of the four visits. Overall efficacy will be examined using a 2X4 (Drug X Time) Repeated Measures Analyses of Variance (ANOVA). The statin/cholesterol vs statin groups will be compared and evaluated for significant differences

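### With lovastatin in both arms and no vehicle or untreated control, the design cannot support the hypothesis that both treatments help, and SAP 6.1 does not name the randomised contrast as the efficacy test

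*Protocol*

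**What the plan says.** **Hypothesis.** Protocol 1.0 states: "Our working hypothesis is that both topical cholesterol/lovastatin and lovastatin alone are helpful". SAP 3 repeats it. The purpose sentence just before it, in both documents, is comparative: the combination against lovastatin alone. SAP 1 gives the same comparative aim.

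**Design.** Protocol 10.0 and SAP 2 describe two randomised groups, cholesterol/lovastatin and lovastatin only. On allocation the protocol says: "They will have a 50/50 chance of being in either group". Neither document describes a vehicle arm, an untreated arm, an untreated control lesion or a historical benchmark.

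**Analysis in the protocol.** The only inferential test is in 11.0, where the before and after photographs come from the same patient, "hence we employ analysis by paired t-test to compare baseline data with data after treatment".

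**Analysis in the SAP.** Section 6.1 opens: "The primary analysis will compare the improvement in DSAP-GASI scores before treatment and after treatment in both groups". It then names a two-by-four Drug by Time repeated-measures ANOVA for overall efficacy, and ends by saying that the two treatment groups will be compared for significant differences. It does not say whether Drug, Time or their interaction is the primary test.

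**Sample size.** The target was about 50 (Protocol 6.0). SAP 2.1 reports 31 enrolled and no formal calculation.

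**The concern.** To say that each treatment helps is to compare it with what would have happened without it. Nothing in the design supplies that comparison. A before-after change contains any drug effect plus everything else that moves the score over 12 weeks. Protocol 3.0 describes ointment applied under occlusion, and DSAP-GASI grades rim elevation, scaling and color (SAP 4.1). An ointment base or occlusion could plausibly change these features without any drug action. Natural course and differences between photographs taken by patients add to this.

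The headline conclusion is at stake. If the before-after result or the Time effect is taken as the efficacy test, shared improvement would be credited to both drugs. If the arms also fail to differ, the data could not distinguish two equally effective treatments from two ineffective ones.

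**Working it through.** **1. What each contrast estimates.** Write the mean improvement from baseline to week 12 as the sum of:

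- N: non-drug change, taken as common to both arms
- L: effect of lovastatin
- C: effect of adding cholesterol to lovastatin

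Then:

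- Group A, before-after: N + L + C
- Group B, before-after: N + L
- Time effect, equal arms: [(N + L + C) + (N + L)] / 2 = N + L + C/2
- Group A minus Group B: C

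The paired test and the Time effect always contain N + L and cannot split the two. The between-arm difference is free of N, but also of L. It therefore answers whether cholesterol adds anything, not whether lovastatin works.

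**2. Size of the problem for the paired test.** The documents give no figure to reproduce: there is no alpha, SD, effect size or power. Inputs:

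- n = 15 and 16 per arm: 31 enrolled (SAP 2.1), with a near-equal split assumed from 1:1 allocation
- n = 25 per arm: 50 / 2 (Protocol 6.0)
- two-sided alpha of 5%: assumed
- L = C = 0, with N = d SDs of the change score and d from 0.2 to 0.8: assumed

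The paired t-test has a noncentral t distribution with n − 1 degrees of freedom and noncentrality d√n. With t the 97.5% point of the central distribution,

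P(significant) = 1 − F(t; n − 1, d√n) + F(−t; n − 1, d√n).

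Examples at d = 0.5:

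- n = 15: t = 2.145, noncentrality 0.5 × √15 = 1.936, P = 0.438
- n = 16: t = 2.131, noncentrality 0.5 × 4 = 2.000, P = 0.465

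| d (assumed) | n = 15 | n = 16 | both arms improved, 15/16 | n = 25 per arm | n = 31 pooled |
|---|---|---|---|---|---|
| 0.2 | 11% | 12% | 1% | 16% | 19% |
| 0.3 | 19% | 20% | 4% | 30% | 37% |
| 0.5 | 44% | 46% | 20% | 67% | 77% |
| 0.8 | 82% | 85% | 70% | 97% | 99% |

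The both-arms column is the product of the two single-arm probabilities in the direction of improvement, for example 0.438 × 0.465 = 0.204. The pooled column uses the paired test as a stand-in for the Time effect. A correctly sized test would give 5%, or 2.5% in the direction of improvement. The error grows with sample size because the test is detecting a real change that is not due to the drugs.

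**3. The randomised contrast under the same conditions.** In 20,000 simulated trials with d = 0.5 in both arms and no drug effect, a t-test on change between arms rejected in 5.1% (25/25) and 5.2% (15/16). Simulation error is √(0.05 × 0.95 / 20,000) = 0.15 percentage points, so both agree with the nominal 5%.

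**The case against.** The strongest reply is that the plan already contains the right analysis. SAP 1 and the purpose sentence of Protocol 1.0 ask the comparative question, and SAP 6.1 specifies a Drug by Time model and a comparison of the groups. The paired t-test appears only in the protocol's data management section, and the SAP presents itself as the more detailed account. This largely stands. A reader might infer that the trial has no valid control, or that the SAP plans only before-after tests. Neither is so. What remains is that SAP 6.1 leads with before-after improvement, ties overall efficacy to a model without naming the deciding term, and leaves the paired test in force in the protocol. The both-treatments hypothesis stands in both documents.

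Other replies also carry weight:

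- **A working hypothesis is a rationale, not a declared test.** Nothing in the documents says that a Time effect will be reported as proof that both drugs work. That is a risk the wording leaves open. Change from baseline can be tested; attributing it to the drugs is what fails.
- **Some mechanisms are not established.** A reader might add regression to the mean or season. The documents say only that the doctor identifies the lesions, not that they are chosen for severity, and they give no seasonal pattern of severity. Occlusion appears in Protocol 3.0 but not in the application instructions of Protocol 10.0 or SAP 2.
- **Photographs and raters are partly handled.** SAP 6 requires standardised images with repeats, and SAP 6.1 has two blinded raters. This limits measurement bias but does not remove real non-drug improvement. The SAP does not say whether raters are blinded to visit order.
- **The per-arm rates overstate a claim about both arms.** At small d, both arms are rarely significant together (1% at 0.2 SD, 4% at 0.3 SD).

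**Conclusion.** The point holds for the hypothesis as written. No analysis of these two arms can show that either treatment helps compared with no drug, and that does not depend on any number. How often a false positive would arise does depend on the unknown non-drug change. Per arm at 15 or 16 patients it runs from about 11-12% at 0.2 SD to 82-85% at 0.8 SD, against a nominal 5%. These rates assume an even split and that all 31 patients are analysed. SAP 6.1 restricts the efficacy analysis to patients with clear photographs at every visit, so the actual numbers may be smaller.

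The comparison of the two arms remains sound as a test of adding cholesterol, provided non-drug change is the same in both arms apart from chance. A non-significant difference should not be read as showing that both worked. With 15 and 16 patients, a two-sided 5% t-test has only 27% power for a true difference of 0.5 SD and 58% for 0.8 SD (assumed effects).

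**What to change.** 1. **Protocol 1.0 and SAP 3:** state the confirmatory hypothesis as the randomised question already in SAP 1, cholesterol/lovastatin against lovastatin alone.
2. **Protocol 11.0:** remove the paired t-test as an efficacy test, so that the protocol agrees with the SAP.
3. **SAP 6.1:** name the between-arm contrast as the primary efficacy test. The Drug by Time interaction already in the model will serve; a baseline-adjusted difference at week 12 is an acceptable alternative. The choice is optional, but one should be named.
4. **SAP 6.1:** state that within-arm change and the Time main effect are descriptive and are not evidence that either treatment works.

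This needs no new patients, visits or data. The sponsor gives up a separate efficacy claim for each arm. There is also a timing cost: 31 patients are already enrolled, researchers are unmasked, and Protocol 13.0 has available efficacy data compiled every other month. The change should therefore be issued as a dated amendment and disclosed in the report, with a statement of what data had been seen when it was made.

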2.0 Background

Porokeratosis is a premalignant condition with a malignant transformation rate of 7.5%¹. Variants include disseminated superficial actinic porokeratosis (DSAP), disseminated superficial porokeratosis, porokeratosis of Mibelli, porokeratosis palmaris et plantaris disseminate, porokeratosis ptychotropa, and linear porokeratosis.

Porokeratosis is a rare condition involving clonal proliferation of abnormal keratinocytes that can be inherited or acquired. DSAP is the most common type of porokeratosis. It is described as a well circumscribed, erythematous macule with a peripheral rim of hyperkeratosis, also referred to as the coronoid lamella. While typically benign, lesions may develop into squamous cell carcinoma or Bowen's disease¹. The lesions typically spare the palms and soles and are most prevalent on the extensor surfaces and back. DSAP typically presents in patients in their 30s and 40s who have a history of extensive ultraviolet radiation exposure. It is estimated to occur in a female to male ratio of 1.8:1².

The exact pathogenesis for DSAP is currently unknown, however, the mevalonate genetic pathways are suspected to play a role in development. In one study, at least one mutation in the mevalonate pathway was found in 98% of familial cases and 70% of sporadic cases³. Treatment usually consists of destruction of the lesion utilizing cryotherapy, photodynamic therapy, carbon dioxide lasers, 5-fluorouracil. However, recent observations have suggested that various porokeratosis variants arise in areas affected by second-hit mutations in genes encoding components of the mevalonate pathway. Consequently, investigators from Yale University successfully treated a series of patients with topical cholesterol/lovastatin which resulted in complete clearance of DSAP lesions after 4 weeks of treatment⁴.

It is hypothesized that statins will block the accumulation of toxic metabolites in the mevalonate pathway, while topical cholesterol will provide the essential nourishment to the cells⁴. This study will provide a larger sample size and allow us to observe more definitive outcomes of the stain/cholesterol therapy.

3.0 Intervention to be studied

Noninvasive in vivo imaging techniques have become an important diagnostic aid for skin cancer detection. Dermoscopy, also known as dermatoscopy, epiluminescence microscopy, incident light microscopy, or skin surface microscopy, is performed using a handheld instrument called a

dermatoscope or dermoscope, which has a transilluminating light source and standard magnifying optics (10×). The dermatoscope facilitates visualization of subsurface skin structures located within the epidermis, dermoepidermal junction, and papillary dermis, which are otherwise invisible to the unaided eye. Colors and structures visible with dermoscopy are required for generating a correct diagnosis.

Dermlite dermatoscopes are approved by the FDA.

We will utilize 2% cholesterol and 2% lovastatin ointment. It will be compounded by a pharmacist. Ointment will be applied on lesional skin with occlusion twice daily. Cholesterol and lovastatin are not approved by the FDA to be used in porokeratosis but are used off-label by physicians for the treatment of DSAP.

Pharmacology

Cholesterol is an animal sterol found in the body tissues (and blood plasma) of vertebrates. It can be found in large concentrations within the liver, spinal cord, and brain. Cholesterol is an important component of the membranes of cells, providing stability. Cholesterol is distributed universally in all animal tissues. It can be derived either from intestinal absorption of dietary cholesterol or from synthesis de novo within the body. Cholesterol itself in the animal system is the precursor of bile acids, steroid hormones, and provitamin D3.

Lovastatin is a lactone metabolite isolated from the fungus *Aspergillus terreus* with cholesterol-lowering and potential antineoplastic activities. Lovastatin is hydrolyzed to the active beta-hydroxyacid form, which competitively inhibits 3-hydroxyl-3-methylglutarylcoenzyme A (HMG-CoA) reductase, an enzyme involved in cholesterol biosynthesis. In addition, this agent may induce tumor cell apoptosis and inhibit tumor cell invasiveness, possibly by inhibiting protein farnesylation and protein geranylgeranylation, and may arrest cells in the G1 phase of the cell cycle. Studies suggest that less than 5% of the oral dose reaches the general circulation as active inhibitors and the time to peak serum concentration is 2-4 hours. Lovastatin undergoes extensive first-pass metabolism so the availability of the drug in the system is low and variable. The peak concentrations of lovastatin when a dose of 10-40 mg is administered are reported to range from 1.04-4.03 ng/ml and an AUC of 14-53 ng.h/ml. This indicates that lovastatin presents a dose-dependent pharmacokinetic profile.

Lovastatin is a HMG-CoA reductase inhibitors that has been used topically for the treatment of skin disorders such as acne, seborrhoea, rosacea, rhinophyma, atopic dermatitis, contact dermatitis and ichthyosis (US Patent 5,730,992 1998 and US Patent 6,126,947 2000). Topical lovastatin at 49 mM (20 mg/ml) in 95% ethanol is well-tolerated with limited side effects. Muscle breakdown may occur resulting in signs and symptoms such as myalgias, fasciculations, cramping, myopathy, rhabdomyolysis and increased levels creatine kinases in the blood. The ethanol component may induce mild skin dryness. It was effective in the treatment of acne vulgaris, thus supporting the expectation of absorption through the skin. Lovastatin is known to cause reversible cell cycle arrest and effective concentrations depend on cell type and experimental conditions, but cell culture

concentrations of 2 to 20 μM (0.8–8.0 $\mu\text{g/ml}$) for up to 72 h result in reversible cell cycle arrest with cells beginning to cycle after 6 hrs^{5,6}.

4.0 Study Endpoints

- Percentage of clearance of disseminated superficial actinic porokeratosis lesions after 12 weeks of therapy
- Validated scale changes: Patient Quality of Life (RAND36, DLQI), Physician Global Assessment Scale (DSAP-PGA), Actinic Keratosis Field Assessment Scale
- Clearance of coronoid lamella on dermoscopy (or photograph) after 12 weeks of therapy.

5.0 Inclusion and Exclusion Criteria/ Study Population

Inclusion Criteria

- All patients 18 years and older with the diagnosis of disseminated superficial actinic porokeratosis.

Exclusion Criteria

- Patients with allergies or contraindications to lovastatin or cholesterol
- Female patients currently pregnant or lactating.
- Patients requiring their medications to be delivered to Alabama (Chemistry Rx does not dispense medications to this state)
- Female patients with plans to become pregnant.
 - Patients actively taking approved forms of long-term contraception (oral contraceptives, implantable intrauterine devices, or other hormone eluting implants) will be allowed to participate as long as they have no plan to become pregnant during the course of the study. A urine pregnancy test will be administered to these patients to confirm that they can be included in the study.

6.0 Number of Subjects

Approximately 50 subjects will be recruited.

7.0 Setting

- **Study Sites**
- Virtual video chat forums with patients living in the USA.
- Medical University of South Carolina
 - Dermatology Clinics

8.0 Recruitment Methods

Recruitment will occur after standard of care visits to the Dermatology Clinics, virtual visits, and chart review of eligible patients.

For standard of care visits, the first person to tell eligible patients about this study will be someone directly involved in their patient care. If they are interested, the aforementioned clinician and study team members will approach the patients without coercion and with the emphasis on the voluntary aspect of being on this study. Subjects will also be told in a caring manner that no matter what their decision is, it will not affect how their doctor cares for them as a patient or their care in general.

Patients discovered via chart review will be contacted to be informed of the potential research opportunity under the same aforementioned conditions. Only patients who have indicated they are willing to be contacted for research opportunities on their MUSC profile will be eligible for this form of contact. In this instance the first person to contact them may not be someone directly involved in their patient care.

Potential subjects who contact the study team members directly will also be considered for participation in the study. In this event, these potential subjects must have heard about the study through indirect information sources (clinicaltrials.gov, DSAP support groups, or other means by which the study team members did not directly advertise the study for purposes of recruitment). If they are interested, the aforementioned study team members will respond to them via email, and subsequently approach the patients virtually without coercion and with the emphasis on the voluntary aspect of being on this study. Subjects will also be told in a caring manner that no matter what their decision is, it will not affect how their doctor cares for them as a patient or their care in general.

9.0 Consent Process

Written informed consent will be obtained from subjects. Informed consent will be obtained in a private room within the clinics or privately via virtual visits. All subjects will undergo a prescreening call by study team members during which they are informed of the details of the study, eligibility concerns, and given the opportunity to ask and questions or address concern about the study. They will be sent the consent form immediately afterward, allowing them ample time to review the document before meeting the study team in person or virtually during visit 1 (week 0). During visit 1, the trained study team member performing consent will then review the consent form with them once again and address any questions before the sign the document and return it to the team via email. Virtual consenting will be performed on REDcap. Only trained research team members will be obtaining informed consent. Training will be performed by [name] and only those who are trained will perform informed consent after they sign the study training log. No waiting period will be necessary between informing the subjects and obtaining the consent; however, subjects will be allowed to take home the unsigned consent form for review prior to signing it if needed.

The virtual consent process for patients who contact study team members directly about potential interest in participating is summarized below:

1. subjects contact our study team after hearing about our study from indirect sources
2. Interested subjects are called by one of our study team members for a prescreening call in which we determine if they are eligible to participate in our study. This is also an

opportunity for Q&A for potential participants who may want eligibility information or details about the study prior to an official enrollment visit.

3. Potential subjects are securely emailed a copy of the IRB-approved ICF and scheduled for an official enrollment video visit that is mutually agreeable for the investigators and potential participant. The time period between this email and the enrollment visit will provide participants ample time to review the ICF in detail so that they have the opportunity to prepare additional questions during the official enrollment visit.

4. Investigators and potential participants engage in a video chat for consenting, in which REDCap will be used for execution of the consent process. Study participants will have the option to have the signed ICF sent to their personal email after it is signed by both parties.

6. Subsequently, Visit 1 will proceed following the procedures in our protocol

